3.3 Randomization

During the enrollment phase (admission to hospital), each subject will be assigned a subject study number. The first subject will be assigned the number 001 and each subject thereafter will be assigned a consecutive number i.e., 002, 003, etc.

In each cohort, subjects will be randomized into 1 of 2 arms in a 1:1 ratio each receiving an interventional treatment.

Arm 1: Subjects administered Proxalutamide 300mg q.d for 14 days + standard of care as determined by the PI at the site

Arm 2: Subjects administered Proxalutamide placebo 300mg q.d for 14 days + standard of care as determined by the PI at the site

In each cohort, each subject will be randomized using an interactive web software: Randomizer.at. The blinding table layout will be a single block. The randomization method used will be permuted blocks of size 4.

This is a blinded study. Neither participants, nor investigators, nor the study team will be aware of treatment assignments prior to the final data base locks at the conclusion of the study (or the interim analysis).

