4.3 Subject Withdrawal

Subjects may withdraw at any time for any reason. In the event the principal investigator or the site monitor believes a subject is at risk of injury the subject will be withdrawn from the study and:

- (a) If the subject has not completed the study
- (b) The subject will be replaced with another subject

- (c) The PI will follow-up with the subject every day for 14 days
- (d) The information will be reported in the appropriate CRF

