7.3 Subject Population(s) for Analysis

- The primary analysis will be based on the intent-to-treat (ITT) population. The data from all subjects enrolled in the study will be analyzed.
- The safety analysis will be based on a modified intent-to-treat (MITT) population i.e., subjects who received at least one dosage of the interventional treatment.
- Subgroup analysis based on: 1) age stratification; and 2) androgen status as defined by the “Gabrin sign” or “PCOS signs” will be conducted for the primary and secondary outcomes.

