7.7 Deviation Reporting

No deviation from the plan will be implemented without the prior review and approval of the EC/IRB.

8 Direct Access to Source Data/Documentation

The PI and hospital will permit trial-related monitoring, audits, IRB/IEC(s) review and regulatory inspection(s) by providing direct access to source data/documentation.

9 Quality Control and Quality Assurance

Every effort will be made to keep staff assignments consistent throughout the entire study. The PI who assesses the subject at baseline should follow the subject throughout the completion of the study. This will ensure that this study is conducted – and that data is generated, documented (recorded), and reported - in compliance with this protocol, with GCP, and any other applicable regulatory requirements. The study monitor will audit the study procedures and CRFs throughout the study.

10 Ethical Considerations

This study will be conducted according to US and international standards of Good Clinical Practice (FDA regulations 21 CFR 312 for IND studies and FDA guidance E6) for all studies. Applicable government regulations and hospital research policies and procedures will also be followed.

This protocol and any amendments will be submitted to the Institutional Review Board (IRB) for formal approval to conduct the study. The decision of the IRB concerning the conduct of the study will be made in writing to the investigator.

All subjects for this study will be provided a consent form describing this study and providing sufficient information for subjects to make an informed decision about their participation in this study. This consent form will be submitted with the protocol for review and approval by the IRB. The formal consent of a subject, using the IRB-approved consent form, will be obtained before that subject is submitted to any study procedure. This consent form must be signed by the subject or legally acceptable surrogate, and the investigator-designated research professional obtaining the consent.

11 Data Handling and Record Keeping

During enrollment, each subject will be assigned a number. The numbers will be consecutive starting at 001.

During enrollment a record will be created for each subject. Each record will contain the subject's demographics, subject's efficacy parameters and any adverse events or study related information.

The subjects' records will be stored and handled in the same manner as the PI's patients' records.

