The study monitor will keep a separate record at the monitor's office of each subject's identification number, the treatment administered to the subject (arm assignment), outcomes and any laboratory results.

No other data will be recorded. No personal information will be kept outside the study site.

Data compiled at the end of the study will not include any information that can be used to identify individuals.

The site will keep all subject records for a minimum of 3 years after the completion of the study.

12 Finance and Insurance

The Principal Investigator will be responsible for the cost of study. The site carries insurance for accidental injury. There is no other insurance.

APPENDIX 1

Drugs that should be used cautiously with Proxalutamide

Strong CYP3A4 inducer
Avamibe, Carbamazepine, Phenytoin, Rifampicin, Mitotan, Nevirapine, Phenobarbital, Rifabutin, Rifapentine, St. John's wort, Alfentanil, Ryclosporin, Dihydroergotamine / Ergotamine, Fentanyl, Irinotecan, Pimozit, Quinidine, Sirolimus, Tacrolimus
Moderate CYP3A4 inducer
Smacet, Tavern, Bosentan, Efaviron, Etruverin, Lopinavir, Modafinil, Nafceillin, Thalidazine, Tiranavir, Ritonavir
Strong CYP3A4 inhibitor
Posidovir, Clarithromycin, Conivatan, Indinavir, Itraconazole, Ketoconazole, lopinavir / Ritonavir, Mibedil, Nefazodone, Nefenavir, Posaconazole, Ritonavir, Saquinavir, Trapivir, Taliomycin, Voriconazole, Etigavir / Ritonavir, Fluconazole, Tiranavir / Ritonavir, Acetamycin
Moderate CYP3A4 inhibitors
Apronavir, Aripitan, Azanavir, Casopitam, Cimetidine, Ciprofloxacin, Clazotinib, Cyclosporin, Dalunavir, Diltiazem, Dronedarone, Erythromycin, Imatinib, Tofesoyang, Verapamil
Sensitive CYP3A4 substrates
Remifentanil, Aripiptam, Budesonide, Buspirone, Conivatan, Daphnesin, Darunavir, Dasatinib, Dronedarone, Eletroptan, Eplerenone, Everolimus, Felodipine, Indinavir, Fluticasone, Lopinavir, Lovastatin, Lulasidone, Maravelo, Midazolam, Nisoldipine, Quetiapine, Saquinavir, Sildenafil, Simvastatin, Sirolimus, Tolvaptan, Tiranavir, Triazolam, Vardenafil
Narrow therapeutic index CYP3A4 Substrate
Astemizole, Cisapride, Cyclosporine, Dihydroergotamine, Fentanyl, Pethidine, Quinidine, Tacrolimus, Terfenadine
Sensitive CYP2D6 substrates
Tomoxetine, Decipamine, Dextromethorphan, Metoprolol, Nebeprolol, Perphenazine, Tolterodine, Venlafaxine, Avamibe, Carbamazepine, Phenytoin sodium, Rifampicin

Narrow therapeutic index CYP2D6 Substrate

Thioridazine

Revision History				

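### Section 11 puts arm assignment in the auditing study monitor's record with no after-lock condition, which conflicts with the blinding statement in Section 3.3

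*Combined protocol and SAP*

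**What the plan says.** All references are to the current protocol (men and women) unless stated.

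- **Section 11, Data Handling and Record Keeping.** The study monitor keeps a separate record, at the monitor's own office, of each subject's number together with "the treatment administered to the subject (arm assignment), outcomes and any laboratory results". No date, access rule or coding is attached.
- **Section 3.3, Randomization.** "Neither participants, nor investigators, nor the study team will be aware of treatment assignments prior to the final data base locks" The sentence continues "at the conclusion of the study (or the interim analysis", so the interim analysis is the only stated exception.
- **Section 9, Quality Control and Quality Assurance.** "The study monitor will audit the study procedures and CRFs throughout the study".
- **Section 4.3, Subject Withdrawal.** "In the event the principal investigator or the site monitor believes a subject is at risk of injury the subject will be withdrawn". The section adds: "The subject will be replaced with another subject".
- **Section 7.3, analysis populations.** The primary analysis is by intention to treat: "The data from all subjects enrolled in the study will be analyzed".

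**The concern.** A monitor who checks outcome forms should not be able to see the treatment beside the outcome. If the monitor can, the choice of which entries to query, how hard to press, and which corrections to accept may differ by arm without anyone intending it. Intention-to-treat analysis cannot repair data altered in that way.

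A second route runs through withdrawal. If the person holding the record can also prompt the removal and replacement of a subject, who stays under full follow-up could come to depend on treatment.

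The investigators treated unblinding as a practical risk in this trial. The final statistical plan, in its rationale for the subgroup analysis by site, says the randomisation scheme at a small remote hospital was changed partly to prevent it.

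**Working it through.** The plan gives no figure on this point and no formula applies, so the check sets the passages side by side.

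1. **Does the record reveal treatment?** Yes. Section 11 names the treatment administered and glosses it as the arm. The arm label is not a masked code, because Section 3.3 defines it openly: "Arm 1: Subjects administered Proxalutamide 300mg q.d for 14 days + standard of care". Arm 2 is defined there as placebo.

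2. **When is the record filled in?** Section 11 does not say. Three features point to completion during the trial:
   - The paragraphs on subject numbering and subject records, earlier in the section, are set at enrolment.
   - Shortly after the monitor's record, the section applies an end-of-study condition to compiled data, but it puts none on the monitor's record.
   - Section 9 has the monitor working throughout the study.

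   In-trial completion is therefore the natural reading, but it is not an explicit statement.

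3. **Is the monitor inside the blind?** Section 3.3 covers participants, investigators and the study team. *Study team* is not defined. No unblinded monitor, separate unblinded role or firewall is described anywhere.

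4. **What can the monitor influence?** Section 9 gives the monitor the audit of procedures and forms. Sections 3.2 and 5.2 give the daily evaluation and the recording of the ordinal scale to the investigator. The direct exposure is therefore through audits, queries and corrections, not through scoring.

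5. **Does the exposure reach withdrawal?** Only conditionally. Section 4.3 refers to a *site monitor*, while Sections 9 and 11 refer to a *study monitor*. The documents neither equate nor separate the two.

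6. **If it does, how far does intention to treat protect?**
   - Section 4.3 gives daily follow-up for 14 days after withdrawal. Counting from withdrawal, a subject withdrawn on day *d* is followed to day *d* + 14, which falls short of day 28 whenever *d* < 14. For example, withdrawal on day 5 gives follow-up to day 19.
   - The day-14 primary endpoint lies within that window.
   - The Section 3.1 outcomes that run to day 28 (clinical status, time to recovery, death) may not.
   - Section 7.1 says only that missing data will be described, so no method fills the gap.

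7. **Where does the conflict come from?** The male-only protocol has the same Section 11 sentence, and its Section 3.3 reserved knowledge of the arm to the sponsor. The revision history records a change of randomisation model on 19 January 2021. Section 3.3 now reads differently, but the Section 11 sentence is unchanged.

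**The case against.** The best defence is that Section 3.3 is the specific blinding rule and controls Section 11, so the arm field would stay empty until lock. On that view Section 11 is leftover text, not a decision to unblind the monitor. This is possible, and the carry-over from the male-only protocol makes it plausible. But the protocol does not say so, and a monitor who followed Section 11 literally would hold the assignments.

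A second defence is that the monitor may fall outside the undefined study team. That would soften the literal contradiction. It would not remove the exposure, because the auditor would still see arm and outcome together.

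Some stronger readings are tempting, but the documents do not support them:

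- **That the outcome assessors were unblinded.** Nothing in Section 11 passes the arm to participants or to the investigators who score the scale.
- **That the monitor could remove subjects knowing their arm.** This requires the two monitor titles to mean one person, or the record to be shared. Neither is stated.
- **That a mortality bias can be calculated.** Take 294 per arm (147 in each of two cohorts) and an assumed 15% mortality, which is about 44 deaths per arm.
   - If nine withdrawn subjects' deaths are lost and no replacement dies, the ratio is (44 − 9)/44 = 0.80.
   - If the nine replacements also die at 15%, it is (44 − 9 + 1.35)/44 = 0.83.
   - If the withdrawn subjects' outcomes are kept, as Section 7.3 and the randomised denominator for deaths in Section 3.1 imply, it stays at about 1.00.

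   The result depends entirely on the assumptions. Neither the 15% nor the nine withdrawals come from the documents.

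**Conclusion.** The point holds as a conflict between Section 3.3 and Section 11, made consequential by the auditing role in Section 9. As written, audit queries and data corrections could be made with knowledge of treatment, and no role or firewall is defined to prevent it.

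The conclusion assumes that the record is filled in during the trial, which is the natural but unstated reading. The literal contradiction also assumes that the monitor belongs to the study team. The extension to withdrawal and replacement holds only if the *site monitor* and *study monitor* are the same person or share the record. In that case intention to treat gives partial protection, weaker for the day-28 outcomes than for the day-14 primary endpoint.

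The size of any bias cannot be estimated from the documents. A reader might infer that the trial was not double-blind in practice, or that its results were biased. The text supports neither inference.

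**What to change.** In Section 11, remove arm assignment from the monitor's record until final database lock, leaving subject number, outcomes and laboratory results. State that the allocation list is held in the randomisation system, or by a named role with no part in monitoring, outcome data or withdrawal. Limit release before lock to the exception already in Section 3.3 and any emergency unblinding. Section 3.3 should also say whether the study team includes the monitor, and Sections 4.3, 9 and 11 should say whether the two monitor titles mean one role. None of this changes a treatment or withdrawal rule.

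Because the final statistical plan dates from manuscript writing, the trial report should also state when the arm field was filled in and who had access to it.

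The cost is minor: a short edit to Section 11, clarifying wording elsewhere, and a small change in who holds the allocation list. The protocol names the web randomisation tool but does not say who keeps the list, so a custodian may have to be designated.

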6.4.3 Reporting Unanticipated Problems to Subjects

Subjects will be informed of any UPs that occur as part of their participation in this trial.

7 Statistical Plan

7.1 *Statistical Methods*

I. General Principles:

- Double-blinded, placebo controlled randomized interventional study with a two-sided type I error rate of 0.05.
- Continuous variables will be expressed as median (interquartile range [IQR]) and categorical variables will be expressed as a number
- 95% confidence intervals will be calculated for the primary outcome
- Group comparisons will be analyzed by the Wilcoxon rank sum test or χ^2 test
- The placebo arm will be used as a reference group when calculating treatment effects
- Differences between rates of clinical improvement will be calculated using unadjusted ordinal logistic regression or Cox proportional hazard models
- Statistical analyses will be conducted using XLSTAT version 2020.5.1 (Addinsoft, Inc.)

II. Statistical Hypotheses:

The primary endpoint is the distribution of clinical assessments on the COVID-19 ordinal scale at day 14. The primary outcome will be analyzed using the Wilcoxon rank sum test.

The Null Hypothesis (H_0) is that the distribution of clinical assessments on the COVID-19 ordinal scale at day 14 among hospitalized COVID-19 subjects treated with Proxalutamide is equal to the distribution of clinical assessments on the COVID-19 ordinal scale at day 14 among hospitalized COVID-19 subjects treated with the Proxalutamide placebo

The Alternative Hypothesis (H_A) is that the distribution of clinical assessments on the COVID-19 ordinal scale at day 14 among hospitalized COVID-19 subjects treated with Proxalutamide is not equal to the distribution of clinical assessments on the COVID-19 ordinal scale at day 14 among hospitalized COVID-19 subjects treated with the Proxalutamide placebo

Mathematically written as:

$$H_0: P(X > Y) = P(Y > X)$$

$$H_A: P(X > Y) \neq P(Y > X)$$

Where X and Y are randomly selected clinical assessments from the two treatment arms in the study.

III. Primary Efficacy Analysis:

- The non-parametric Wilcoxon rank sum test (Mann Whitney U) will be used to assess the primary end point.
- P-values <0.05 will be considered significant. All statistical analysis will be based on the intent-to-treat (ITT) population. All missing data will be described.

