7.2 Sample Size Estimates

Assumptions:

- The sample size estimation is based on the results reported in the placebo arm of the Adaptive COVID-19 Treatment Trial (NCT04280705)
- On day 15, 61% of subjects in NCT04280705 placebo group remained hospitalized.
- The odds ratio of improvement in the ordinal scale in the Proxalutamide arm compared to the Proxalutamide placebo is at least 2.0
- The study has two arms with randomization at 1:1 ratio
- 90% power to detect an odds ratio of 2.0 using a two-tailed test with a type I error rate of 5%
- According to NCT04280705 protocol “The sample size to detect a given odds ratio for 1:1 randomization using a 2-tailed test at level α is estimated by the equation below. λ is the log odds ratio, p_i is the overall probability (combined over both arms) of being in the i th category of the K ordinal outcomes, and $z_{\alpha/2}$ and z_{β} are the $1 - \alpha/2$ and $1 - \beta$ quantiles of the standard normal distribution.”

$$\frac{12(z_{\alpha/2} + z_{\beta})^2}{\lambda^2(1 - \sum_{i=1}^K p_i^3)}$$

- The estimated distribution is based on NCT04280705 protocol scenario 4
- 3.5% of the subjects will not complete the study based on NCT04280705

Sample Size Estimate:

CONFIDENTIAL

This material is the property of the Applied Biology Inc. Do not disclose or use except as authorized.

Based on the assumptions above, we calculated that at a minimum we would need to recruit for each cohort 294 subjects (147 subjects in each arm) i.e., a total of approximately 600 subjects.

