Revision	Description of Change		Date	Signature
1	New draft release	[name]	Dec 27, 2020	
2	Amendments to end points	[name]	Dec 29, 2020	
3	Amended AE section	[name]	Dec 30, 2020	
4	Amended to include female cohort	[name]	Jan 10, 2021	
5	Final review for female cohort	[name]	Jan 10, 2021	
6	Added exclusions for sexual activity and minor corrections	[name]	Jan 11, 2021	
7	Changed randomization model	[name]	Jan 19, 2021	
8	Amended inclusion criteria	[name]	February 1, 2021	

CONFIDENTIAL

This material is the property of the Applied Biology Inc. Do not disclose or use except as authorized.

FINAL STATISTICAL PLAN WITH SUMMARY OF CHANGES FROM THE FINAL PROTOCOL

We had to make minor adjustments to the statistical plan of the final protocol while writing the manuscript to make the statistical plan more stringent and clearer. The rationale for each change or no change is also presented.

Table of contents:

1. Primary Outcome Measure.....	1
2. Secondary Outcome Measures	2
3. General principles.....	4
4. Statistical hypothesis	5
5. Primary analysis efficacy.....	6
6. Sample size calculation	7

1. Primary Outcome Measure

Proposed in the final protocol	Final statistical Plan	Rationale
Treatment efficacy of proxalutamide relative to placebo arm as assessed by the COVID-19 ordinal scale [time frame: day 14]	No change	The distribution analysis of all the COVID-19 8-point ordinal scale scores at day 14 covers all possible scores, 1 to 8. This is better illustrated graphically for group comparison.
No specific measure of effect was appointed for the Primary efficacy analysis (quantitative efficacy measure).	Recovery ratio was defined as the measure of effect for the primary outcome. The treatment efficacy of proxalutamide was assessed by the proportion of recovered patients in both study arms [time frame: 14 days]. Recovery was defined as reaching scores 1 and 2 in the COVID-19 ordinal scale	Scores 1-2 represent a clear cut for recovery (alive hospital discharge).

2. Secondary Outcome Measures

As proposed in the final protocol	Done in the final statistical Plan	Rationale

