Treatment efficacy of Proxalutamide relative to placebo arm as assessed by the COVID- 19 ordinal scale (defined in Section 5.1) [Time Frame: Day 28]	A clear cut-off point was used in the COVID-19 scale (scores 1 and 2) so that we were able to measure the effect size recovery ratio [time frame: 28 days].	All scores at Day 28 are informative and is better presented in a graph. As reported for the primary outcome, we clarified a measure of effect within this secondary outcome measure.
Time to recovery [Time Frame: Day 1 through Day 28] Recovery is defined as the first day on which the subject satisfies one of the following two categories from the ordinal scale.1): 2) Not hospitalized, limitation on activities and/or requiring home oxygen; 1) Not hospitalized, no limitations on activities.	Name changed to post-randomization time to recover/alive hospital discharge [time frame: day 1 to day 28] in median days (interquartile range). Recovery was defined as the first day on which the subject reached scores 1 and 2 in the COVID-19 ordinal scale.	We needed to be more specific in this outcome to make it clearer and reproducible.
Proportion of death [Time Frame: Day 1 through Day 28] Defined as the number of subjects who have died in each arm divided by the numbers of subjects randomized to the treatment arm	Name changed to 28-day all-cause mortality rate . The proportion of patients who reached score 8 in the 19-COVID ordinal scale after randomization. [Time frame: 28 days]	The outcome is still the same described in the statistical plan of the final protocol, however we just clarified that it refers to all-cause mortality. All-cause mortality is a more stringent measure, and therefore this change goes against the direction of the bias. Although mortality at 14 days could be contemplated in the original Primary outcome (score 8), we decided to analyze mortality at 28 days only, which is more stringent and reflects the intention-to-treat.
Duration of new oxygen use [Time Frame: Day 1 through Day 28]	Excluded	This outcome measure was not adequately reported by the hospital sites, and therefore we have not included it in the final statistical plan.
Proportion of subjects testing positive for SARS-CoV-2 [Time Frame: Day 14]	Excluded	This outcome also needed to be abandoned because we lacked financial resources to test all patients again for SARS-CoV-2 at day 14.

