Differences between rates of clinical improvement will be calculated using unadjusted ordinal logistic regression or Cox proportional hazard models	We used Kaplan-Meier's survivor function for estimates of proportion surviving, and failure function for estimates of alive hospital discharges. Cox proportional hazards model was kept only to calculate hazard ratio (HR) for death and its 95% confidence interval (CI). Graphical assessment and Kaplan-Meier versus predicted survival showed that of the proportional-hazards assumption has not been violated	For better demonstration of the 95% CI and timeline of the evolution of the outcomes in figures. For measure of effect, as stated in the Primary and Secondary outcomes, we adopted relative risk (or Risk Ratio) for easier understanding.
Statistical analyses will be conducted using XLSTAT version 2020.5.1 (Addinsoft, Inc.)	Statistical analysis was conducted using Stata/SE version 16.1 for Mac (StataCorp LLC, College Station, TX, USA).	Preference of the team performing statistical analysis

4. Statistical hypothesis

As proposed in the final protocol	Done in the final statistical Plan	Rationale

The primary endpoint is the distribution of clinical assessments on the COVID-19 ordinal scale at day 14. The primary outcome will be analyzed using the Wilcoxon rank sum test.
	
The primary efficacy endpoint was described as the overall 14-day recovery ratio. This effect measure was obtained after dichotomization of the COVID-19 ordinal scale for scores 2 and 1, representing patients that were discharged from hospital.
	
Although the distribution is still presented graphically, and tested for statistical significance, a clear cut-off point in the COVID-19 ordinal scale was used to obtain the Overall Recovery Ratio. Recovery ratio is a clinically meaningful effect measure.

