
No measure of effect
	
Included measure of effect: Overall Recovery Ratio [time frame: 14 days]
	
Although we meant to calculate the overall recovery ratio, the outcome was not clearly described in the statistical plan of the protocol, and sample size was based on odds ratio for recovery.

6. Sample size calculation

As proposed in the final protocol	Done in the final statistical Plan	Rationale

The sample size estimation is based on the results reported in the placebo arm of the Adaptive COVID-19 Treatment Trial (NCT04280705) protocol scenario 4: On day 15, 61% of subjects in NCT04280705 placebo group remained hospitalized. For 90% power to detect an odds ratio of 2.0 using a two-tailed test with a type I error rate of 5%, and 3.5% of the subjects will not complete the study based on NCT04280705
	
No change.
 
However, we noticed that the way the sample size estimation was described may be hard for many readers to follow it.
 
An odds ratio for improvement of 2 over a baseline recovery risk of 39% (NCT04280705, scenario 4), results in a difference of 14% in the absolute recovery rate. The sample size was calculated to be able to detect a difference of 14% in Overall Recovery Rate at 14 days (risk ratio of 1.36) with a power of 90% and a type I error of 5%, over the estimated 39% recovery rate for the placebo group, and 3.5% non-compliance/cross over in the study groups.
	
Although no change was done in the sample size estimate, we rewrote it using simpler and more direct terms.

Sample size estimate: Based on the assumptions above, we calculated that at a minimum we would need to recruit for each cohort 294 subjects (147 subjects in each arm) i.e., a total of approximately 600 subjects.
	
No change
	
We verified that the sample size was still 90% powered after inclusion of baseline score 6 to the final protocol.

These minor changes in the statistical analysis plan were performed while writing the manuscript.

Researchers involved in the statistical analysis that implemented the changes:

[name], MD, PhD

[name], DDS, PhD

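### The final plan keeps a sample size built on an ordinal-scale odds ratio of 2.0 but drops the model that would estimate it, leaving the scores 1–2 recovery ratio as the only effect estimate for the scale at Day 14 and Day 28.

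*Combined protocol and SAP*

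**What the plan says.** **Protocol 7.1, General Principles.** "Differences between rates of clinical improvement will be calculated using unadjusted ordinal logistic regression or Cox proportional hazard models". The same list makes placebo the reference for treatment effects and promises 95% confidence intervals for the primary outcome, without naming the parameter. Part III, on the primary efficacy analysis, names only the Wilcoxon rank sum test.

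**Protocol 7.2.** Among the sizing assumptions: "The odds ratio of improvement in the ordinal scale in the Proxalutamide arm compared to the Proxalutamide placebo is at least 2.0". The formula there is written for K ordinal categories and a log odds ratio. The result is 294 subjects per sex cohort, about 600 in total.

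**Final statistical plan.**
- Section 1 says of the protocol: "No specific measure of effect was appointed for the Primary efficacy analysis (quantitative efficacy measure". It then defines the recovery ratio (scores 1 and 2) as the Day 14 measure. Section 2 does the same for the Day 28 scale.
- Section 3, in the row that replaces the 7.1 regression line, gives Kaplan-Meier estimates and adds: "Cox proportional hazards model was kept only to calculate hazard ratio (HR) for death". The rationale in that row adopts the relative risk. Ordinal logistic regression does not reappear.
- Section 4 says the Day 14 distribution is still graphed and tested.
- Section 5 states without qualification that the protocol had no effect measure, and adds that "sample size was based on odds ratio for recovery".
- Section 6 marks the sample size as unchanged.

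The plan says that these changes were made during manuscript writing.

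**The concern.** A trial sized to detect a given parameter should report an estimate of that parameter with its interval. Here the design value is still an odds ratio of 2.0 across the ordinal scale, yet no analysis in the final plan estimates it. The whole-scale test that is kept gives a p-value without an effect size. The one effect estimate taken from the scale treats every score from 3 to 8 alike.

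The timing makes the stated reason important. The recovery ratio was chosen after data collection, on the ground that the protocol had left the effect measure open. If the protocol pointed to an ordinal model and an ordinal odds ratio, a reader should be told so. What is at stake is some precision, a direct link from the result to the design, and an accurate account of what was planned.

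**Working it through.** **1. Do the protocol passages fit together?** Set side by side, they point to a common odds ratio: an ordinal endpoint at Day 14 (7.1 II), ordinal logistic regression with placebo as reference (7.1 I), and sizing on a log odds ratio over ordinal categories (7.2). For a score at a fixed day, ordinal regression is the natural choice of the two models listed, because Cox needs a time to event. No sentence, however, names the odds ratio as the primary effect measure.

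**2. The plan's own figure.** The inputs from 7.2 are two-sided α = 0.05, power 90%, odds ratio 2.0, 1:1 allocation and 3.5% not completing.

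N = 12(z_{α/2} + z_β)² / [λ²(1 − Σp³)], with λ = ln 2

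12 × (1.960 + 1.2816)² / (0.6931)² = 262.4, so N = 262.4 / (1 − Σp³).

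The stated 294 leaves 294 × 0.965 = 283.7 completers, which implies Σp³ = 1 − 262.4/283.7 ≈ 0.075. The category probabilities (scenario 4 of the cited trial) are not in the documents. So 294 is consistent with the formula but cannot be confirmed.

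**3. Variance of the log odds ratio with the full scale.** The formula implies 12 / [N(1 − Σp³)] = 12 / (0.925N) = 12.97/N.

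**4. Variance after the scores 1–2 split, by the same formula.** Placebo recovery is 39% (61% still hospitalised, 7.2). An odds ratio of 2.0 gives odds of 2 × 0.39/0.61 = 1.279, or 56.1%. The pooled proportion is (0.39 + 0.561)/2 = 0.476. With two categories, Σp³ = 0.476³ + 0.524³ = 0.252, and the variance is 12 / (0.748N) = 16.04/N.

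**5. Information kept.** 12.97 / 16.04 = 0.81. The equivalent loss is 294 × 0.19 ≈ 56 subjects per cohort.

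| Assumed Σp³ | Information kept by the split | Equivalent loss out of 294 |
|---|---|---|
| 0.03 | 77% | 67 |
| 0.075 (implied by 294) | 81% | 56 |
| 0.15 | 88% | 35 |

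**6. Effect on the interval.** For an estimated odds ratio of 2.0, the CI is 2.0 × exp(±1.96√variance).

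| Subjects | Full scale | Split |
|---|---|---|
| 294 (one cohort) | √(12.97/294) = 0.210; 1.33–3.02 | √(16.04/294) = 0.234; 1.27–3.16 |
| 588 (both cohorts) | √(12.97/588) = 0.149; 1.49–2.68 | √(16.04/588) = 0.165; 1.45–2.76 |

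**The case against.** **The protocol had not fixed a measure.** The regression line sits under General Principles, offers Cox as an alternative, refers to undefined rates of clinical improvement, and mentions neither Day 14 nor Day 28. The odds ratio in 7.2 is a sizing assumption. This stands. A reader might infer that the protocol had pre-specified the common odds ratio as the primary effect measure and that section 1 of the final plan is therefore false. The text does not support that: section 1 says only that no specific measure was appointed for the primary efficacy analysis, and 7.1 III indeed names only a test. The objection does not rescue the unqualified denial in section 5.

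**A summary of changes describes superseded text.** True, and the removal of ordinal regression is shown openly with a reason. But the gap is in the current plan, which keeps the sizing basis and lacks the estimate. The description of the protocol is also offered as the current justification.

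**The design effect can be recovered, and little is lost.** Counts and percentages are reported, so a reader can form the odds ratio at the recovery cut. Under proportional odds this is the same parameter as the common odds ratio. That stands as a partial answer: comparison with the design is possible, but less precise and left to the reader. It would also be wrong to infer that death is ignored or the scale abandoned. The 28-day mortality rate and a hazard ratio for death are reported, and the Day 14 distribution is graphed and tested.

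**The efficiency loss can be made to look larger.** Putting arm-specific variances on the binary side gives (2/N)[1/(0.39 × 0.61) + 1/(0.561 × 0.439)] = 16.53/N and 78% kept, but that compares unlike variances. With one formula on both sides, the figure is 81%.

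**Conclusion.** The point holds as a gap in estimation together with an inaccurate account of the protocol. The final plan retains an ordinal odds ratio of 2.0 as its design basis, removes the model in 7.1 that would estimate it, and puts in its place an effect measure chosen during manuscript writing.

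The cost in precision is modest: about 19% of the information, or some 56 of 294 subjects per cohort. This rests on proportional odds, 39% placebo recovery, a true odds ratio of 2.0, and Σp³ back-solved from 294. No bias in the recovery ratio is shown by this calculation.

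On wording, the sentence in section 1 is narrowly defensible but incomplete. The flat statement in section 5 is not defensible. The parameter section 5 attributes to recovery is, in 7.2, the odds ratio of improvement on the ordinal scale. This should be changed, but it does not by itself undermine the trial's result.

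**What to change.** 1. Report the common odds ratio with 95% CI, placebo as reference, from unadjusted ordinal logistic regression at Day 14 and at Day 28. Give it for each sex cohort (the unit of sizing in 7.2) and overall, with a check of the proportional-odds assumption.
2. Describe it as the estimate that matches the ordinal endpoint, the model listed in 7.1 and the design in 7.2, not as the protocol's formally designated primary measure.
3. Show the recovery ratio beside it, labelled as added while the manuscript was written.
4. In sections 1 and 5 of the final plan, state that 7.1 listed ordinal logistic regression or Cox and that 7.2 used an ordinal odds ratio. Replace the reference to recovery with improvement on the ordinal scale.

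The cost is one additional model per time point, run by cohort and overall on data already collected, plus a few sentences. The sample size does not change. The drawback is reliance on proportional odds. If the check fails, the common odds ratio should be read as an average across cut-points, alongside the full distribution.
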